Primary Aim 1: To test whether CPT is more effective than IDC in treating symptoms of PTSD among Veterans and civilians with OUD maintained on buprenorphine. PTSD symptoms will be measured using the PTSD Checklist – Military version (PCL-5), and confirmed by the Clinician Administered PTSD Scale using the DSM-5 criteria (CAPS-5).

Secondary Aim 1: To test whether CPT- is more effective than IDC in reducing opioid use among Veterans and civilians with PTSD and comorbid OUD maintained on buprenorphine. Opioid use will be measured using the Timeline Follow-back (TLFB) and confirmed by urine toxicology results.

Exploratory Aims: To examine if treatment groups differ in 1) *retention*, measured by days in treatment, 2) *psychosocial functioning*, measured by the *participants RAND 12-Item Short Form Health Survey (VR-12)*, 3) *sleep* as measured by the *Insomnia Severity Index (ISI)*, since sleep disturbance is a hallmark of PTSD and during early abstinence from opioids, and 4) Because of the high comorbidity between PTSD and chronic pain we will explore this relationship and will measure *pain intensity* (measured by the Numeric Rating Scale (NRS), and *functional impairment* using the PROMIS-29 (Patient-Reported Outcomes Measurement Information System) longitudinally over the course of treatment. Follow up will be conducted 1 and 3 months after completion of the study to evaluate *durability of effect on PTSD symptoms (measured as changes in PTSD symptoms), opioid use and treatment utilization*.

4-5. BACKGROUND AND SIGNIFICANCE:

This proposal was originally developed in collaboration with the Consortium to Alleviate PTSD (CAP) ([name] Director and [name] co-Director), underwent scientific review and was proposed for funding. However, CAP was unable to fund it as buprenorphine treatment is of limited importance for active-duty personnel. The CAP leadership group encouraged our group to send this application to the VA as it has great clinical relevance for the VA and for Veterans, *although CAP is no longer involved in this proposal*. Please see the attached letter of support.

A. Posttraumatic stress disorder (PTSD)

i) PTSD is a serious psychiatric disorder that can occur after the experience of a traumatic event.

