6. RESEARCH PLAN

Research design and methods

Overview: We propose to conduct a randomized, controlled trial with 160 (assuming a 30% drop out rate, for 120 participants) Veterans and civilians diagnosed with PTSD and comorbid OUD. This study will use *open*

randomization to 2 groups: (a) buprenorphine + CPT vs. (b) *buprenorphine + IDC*. All subjects will be maintained on buprenorphine and the standard clinical treatment. Participants will be recruited primarily through the clinical facilities at the VA and from other collaborators.

The Bedford VAMC has been added as an additional enrollment site for this study. The principal investigator for the Bedford site is [name] and the study will be overseen by the Bedford VA IRB has gained local IRB approval.

Experimental subjects: Veterans and civilians (n=160) aged 18- 65 years old, with a current diagnosis of PTSD and opioid use disorder (OUD) will be enrolled at 2 sites (VA Connecticut Healthcare System, Bedford VAMC) for a study with 12-weeks of active treatment. Participants will be recruited from four main sources: 1) from the PTSD clinic patients at the local VAs , 2) from the group of Veterans entering treatment for opioid use disorders at the local VA Substance Abuse Treatment Programs and 3) advertisement (flyers, posters, Craigslist) 4. Community clinics. Under a HIPAA waiver, IRB-approved letters of invitation can be mailed to prospective participants with a past diagnosis of OUD or PTSD who otherwise might meet eligibility criteria. Outreach will also be conducted at local Veteran Centers, where staff from both VAs consult. The PTSD staff has also been involved in outreach to the community for returning OIF/OEF Veterans. Each participant will be carefully screened and assessed using the following inclusion and exclusion criteria:

Inclusion Criteria:

- 1) Male and female Veterans and civilians between the ages of 18-70 years old.
- 2) Current diagnosis of PTSD as determined by an independent evaluator assessment using CAPS-5.
- 3) Opioid Use Disorder diagnosed by Mini International Neuropsychiatric Interview for DSM-5 (MINI). To meet entry criteria for buprenorphine treatment, will also have documented prior treatment for opioid use disorder, history of opioid withdrawal or signs of opiate withdrawal as evidenced by a Clinical Opiate Withdrawal Scale (COWS) score of 7 or greater, and a positive urine toxicology for opioids.

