Subject Payment. All participants will be compensated for their participation. Participants will be paid \$30 for the initial screening/baseline assessment. They will be compensated \$30 for each medication visit (x7), and \$45 for follow up visits. There will be no payment for therapy sessions. Individuals can receive up to a total of \$330 if attending all scheduled treatment and visits. Payment will be made through electronic funds transfer (EFT). Participants will need to provide us with your banking information by completing a special payment form. Alternatively, if participants do not have a bank account, a check will be mailed to them instead. This check(s) will be mailed to the address they provide us with. Patients may choose to receive gift certificates issued to them for use at the VCS canteen (retail store) or VCS cafeteria here at the VACHS in lieu of EFT/check payment. If a patient chooses to receive payment by gift certificate they will be paid for the telemedicine/telehealth visits they participated in at their next in-person visit (e.g. if they complete weeks 2 and 3 by telephone they will receive gift certificates for weeks 2, 3, and 4 at the week 4 visit). Study payments are subject to withholding for outstanding federal debts (i.e., defaulted student loans, interstate child support, back taxes etc) without notification.

Power analysis: The sample size calculation for our primary hypothesis (change in PTSD symptoms) was based on findings from one of the largest and most comprehensive meta-analysis reports on PTSD treatment to date.[36] The report evaluated N=112 studies and reported on 137 comparisons, using validated PTSD symptom measures. The meta-analysis reported that the *effect sizes* for psychotherapy when contrasted with a control group were consistently large and averaged $g=1.14$. Three studies administered CPT specifically and the overall effect size for those was large and averaged $g=1.69$. For this study we conservatively are basing our calculations on a moderate effect size by Cohen's definition.[95] For the First and Second Primary aim we estimate that with 60 subjects randomized to each group we have 80% power to detect a medium effect size ($f=0.25$) at two-sided alpha level of 0.05, and assuming 25% dropout we will recruit a total of N=160.]

Data Analysis:

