Study data will be collected and managed using REDCap electronic data capture tools hosted at VA CT Healthcare System. REDCap (Research Electronic Data Capture) is a secure, web-based application designed to support data capture for research studies, providing 1) an intuitive interface for validated data entry; 2) audit trails for tracking data manipulation and export procedures; 3) automated export procedures for seamless data downloads to common statistical packages; and 4) procedures for importing data from external sources.

Descriptive statistics and graphs will be used to summarize the data on all randomized subjects. All continuous variables will be examined for adherence to the normal distribution using normal probability plots and Shapiro-Wilk tests. Transformations will be applied if needed. If normality is not satisfied and transformations do not help with achieving normality alternative analytic strategies will be considered such as generalized estimating equations (GEE) or nonparametric methods for repeated measures analysis. Baseline demographic and clinical characteristics for the two randomized groups (e.g., age, gender, severity of PTSD, and opiate use) will be compared using chi-square tests for categorical variables and t-tests or nonparametric tests for continuous variables. If there are baseline differences between study treatment groups, these variables will be used as covariates in the mixed-effects models analyses described below. Drop outs and completers will also be compared on baseline characteristics using the same approach. Between group differences in treatment retention, medication compliance and frequency of the occurrence of side effect symptoms across the treatment period will also be assessed. Residual plots and other diagnostics will be used to assess model assumptions.

The primary analyses will be intent-to-treat but sensitivity analyses on completers and non-completers will also be performed. All statistical testing will be at a two-tailed alpha level of 0.05. *Adjustments for multiple comparisons will be conducted among measures in specific domains. In the case of PTSD symptoms (use of 2 measures, PCL-5 and CAPS-5) and opiate use (use of TLFB and urine toxicology) the level of significance will be adjusted to 0.025.*

Primary and Secondary Hypotheses:

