For the primary and secondary hypotheses, we will use mixed effects models to assess changes in PTSD symptoms and opiate use over time. Treatments will be used as between-subject factors and time (in weeks) will be used as a within-subject factor. The primary outcome variables will be PTSD symptoms as measured by generated from the PCL-5 and CAPS scales. The secondary outcome variables will be frequency of opiate use generated from the TLFB and confirmed with urine toxicology results each medication visit (weeks 1-4, 6, 8, 12) and follow-up. The use of the mixed-effects models approach for the analysis of our longitudinal data has several specific advantages. Unlike traditional repeated measures analyses, mixed effects models allow for different numbers of observations per subject, use all available data on each subject and are unaffected by randomly missing data. They also provide flexibility in modeling the correlation structure of the data.[96]

Primary Aim 1. We hypothesize that CPT will significantly reduce PTSD symptoms compared to IDC in Veterans and civilians with PTSD and comorbid OUD maintained on buprenorphine.

This hypothesis will be tested by the interaction of treatment (CPT vs. IDC), and time in the mixed model specified above. Significantly greater decrease in PTSD symptoms in the CPT group will be considered supportive of the hypothesis.

Secondary Aim 1. We hypothesize that CPT will significantly reduce opioid use compared to IDC in Veterans and civilians with PTSD and comorbid OUD maintained on buprenorphine.

This hypothesis will be tested by the same approach as described in primary aim 1 but with frequency of opioid use as the dependent measure.

Exploratory Hypothesis:

We hypothesize that CPT will significantly improve retention (days in treatment) compared to IDC in Veterans and civilians with PTSD and comorbid OUD maintained on buprenorphine.

This hypothesis will be tested using ANOVA or nonparametric equivalent comparing the two treatment groups (CPT vs. IDC).

We hypothesize that CPT will significantly improve psychosocial functioning (measured by the VR-12 survey) compared to standard counseling in Veterans and civilians with PTSD and comorbid OUD maintained on buprenorphine.

This hypothesis will be tested by the interaction of treatment (CPT vs. IDC) and time.

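### Power is stated at alpha 0.05, but each of the two primary PTSD measures is tested at 0.025; no rule says whether one or both must pass, and the dropout figures disagree

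*Combined protocol and SAP*

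**What the plan says.** All of the following is in the combined protocol and SAP; the first four points are in section 6.

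- **Power analysis.** The sample size rests on the statement that "with 60 subjects randomized to each group we have 80% power to detect a medium effect size ($f=0.25$) at two-sided alpha level of 0.05". The sentence opens "For the First and Second Primary aim we estimate" and ends "assuming 25% dropout we will recruit a total of N=160".
- **Data Analysis.** Testing is two-tailed at 0.05 in general. For PTSD symptoms (PCL-5 and CAPS-5), and likewise for opioid use (TLFB and urine toxicology), "the level of significance will be adjusted to 0.025".
- **Primary and Secondary Hypotheses.** "The primary outcome variables will be PTSD symptoms as measured by generated from the PCL-5 and CAPS scales". The test is the treatment-by-time interaction in a mixed model, and the only criterion given for Primary Aim 1 is: "Significantly greater decrease in PTSD symptoms in the CPT group will be considered supportive of the hypothesis".
- **Overview.** The enrolment target is "160 (assuming a 30% drop out rate, for 120 participants".
- **Specific Aims (section 3).** There is one primary aim, on PTSD symptoms. It describes the CAPS-5 as confirming the PCL-5 but does not define confirmation. Opioid use comes under "Secondary Aim 1: To test whether CPT- is more effective than IDC in reducing opioid use".

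**The concern.** The sample size was justified at one significance level and the primary measures will be tested at a stricter one, so the stated 80% applies to neither primary test.

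The second gap matters more for interpretation. With two primary measures, the power for Aim 1 depends on whether success on one is enough. Halving alpha points to an either-measure rule, while the aim's language of confirmation points to both; neither is stated. If the PCL-5 reached 0.025 and the CAPS-5 did not, or the reverse, the plan could not say whether Aim 1 was supported, and the choice would be made after the results were known.

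The dropout mismatch bears on how many participants the calculation can count on. The reference to a second primary aim leaves unclear which aims the power statement covers.

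**Working it through.** **Inputs.** From the Power analysis: f = 0.25, 60 per group, two-sided 0.05, 80% power, 25% dropout, N = 160. From Data Analysis: 0.025 per PTSD measure. From the Overview: 30% dropout. For two equal groups d = 2f = 0.50.

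**Reproducing the stated power.** Two-sample t-test with n per group: noncentrality = d × √(n/2) = 0.50 × √30 = 2.739, with 2 × 60 − 2 = 118 degrees of freedom.

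- Two-sided 0.05: 77.5% by the noncentral t, 78.2% by the normal approximation. The stated 80% is therefore about 2.5 points high on its own inputs by the exact method, and within 2 points by the approximation.

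**Power at the level to be used.**

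| n per group | alpha | Power per measure (noncentral t) | Detectable d at 80% power |
|---|---|---|---|
| 60 | 0.05 | 77.5% | 0.52 |
| 60 | 0.025 | 68.0% | 0.57 (f = 0.28) |
| 56 (30% dropout) | 0.025 | 64.6% | 0.59 |

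The normal approximation gives 69.0% for 60 per group at 0.025. Of the 12-point gap to 80% (80 − 68.0), 9.5 points come from alpha (77.5 − 68.0) and 2.5 from the stated figure already being high (80 − 77.5).

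**Power for Aim 1 under each possible rule.** Assumptions not in the documents: d = 0.50 on both measures, and a correlation of 0.5 to 0.8 between the two test statistics. Each measure is tested at 0.025. P(either) = 2 × P(one) − P(both). Ranges span the two correlations and two methods (simulated t-tests and the bivariate normal).

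| n per group | Either measure suffices | Both must pass |
|---|---|---|
| 60 | 77–84% | 53–60% |
| 56 | 74–81% | 49–56% |

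Over a wider correlation range of 0 to 0.9, with 60 per group and the bivariate normal, the either-measure figure falls from 90% to 75% and the both-measures figure rises from 48% to 63%.

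**How far the two-group basis may be from the planned model.** The protocol gives no within-subject correlation (rho). As an illustration, take d = 0.50 in raw-score SD units, a baseline-to-end change, 60 per group and 0.025. For a change score, d_change = 0.50 / √(2(1 − rho)). If the model instead adjusts for baseline, d_adj = 0.50 / √(1 − rho²).

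| rho | Change score | Baseline-adjusted |
|---|---|---|
| 0.3 | 52% | 73% |
| 0.5 | 68% | 81% |
| 0.6 | 78% | 87% |
| 0.7 | 90% | 94% |

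If all 160 randomized (80 per group) had complete end-of-treatment data, the two-group figure at 0.025 would be 81.5%.

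**Dropout.** 160 × 0.75 = 120, as in the Power analysis. 160 × 0.70 = 112, not the 120 in the Overview. Keeping 120 at 30% dropout would need 120 / 0.70 = 171.4, so 172.

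**The case against.** The strongest objection is that 68% is not the power of the planned analysis. That analysis is an intent-to-treat mixed model, which uses partial data from dropouts and gains from correlation between repeated measures. Its power could be above 80%, and the two measures need not have the same power, since the CAPS-5 is collected less often than the PCL-5. This stands as a limit on the figure: 68% is a benchmark on the protocol's own basis. It does not rescue the stated 80%, which uses the same two-group basis at the wrong alpha and gives no correlation from which mixed-model power could be derived. The 81.5% bound requires no missing end-of-treatment data, contrary to the protocol's own dropout assumption.

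Second, splitting alpha is needed only if either measure may carry the aim. On that reading Aim 1 power is about 77–84%, which brackets 80%, and pairing a split alpha with a both-must-pass rule is stated nowhere. That is fair, and the either-measure reading is the more natural one. But the plan does not state it, and the aim's confirmation wording pulls the other way.

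Third, the practical shift is small: detectable d moves from 0.52 to 0.57, and the cited meta-analytic averages (g = 1.14 and 1.69) are far larger. At d = 0.60 power per measure at 0.025 is already 84%. This limits the severity, but the protocol chose a medium effect deliberately, so its power claim should hold there.

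The second-primary-aim label is clerical and adds no weight.

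**Conclusion.** The concern holds. The mismatch between 0.05 and 0.025 and the dropout error follow directly from the text and need no assumption. On the protocol's two-group basis, power is 68.0% per measure at 0.025, against a stated 80% that is itself 77.5% when recomputed.

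Power for Aim 1 is undefined until a success rule is stated. Under the assumptions in the working, the choice of rule moves it by about 18 to 29 points: 78% against 60% at correlation 0.8, and 84% against 55% at 0.5, by the bivariate normal.

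Type I error is protected by the split and the design is not invalidated. What needs correcting is the stated power, the missing rule and the dropout figure.

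**What to change.** 1. Restate power at 0.025: about 68% per measure for f = 0.25 with 60 per group or, equivalently, 80% for d of about 0.57. If power is claimed for the mixed-model interaction instead, give the assumed within-subject correlation, the time points and how baseline is handled, separately for PCL-5 and CAPS-5.
2. State before results are known whether Aim 1 succeeds on either measure or requires both. Give the matching power (about 77–84% or 53–60%) with its assumed correlation and effect on each measure, and say what the confirming role of the CAPS-5 means for that rule.
3. Use one dropout figure throughout: with 160 enrolled, 25% leaves 120 and 30% leaves 112. If 30% is kept, recompute power on 56 per group.
4. Replace the reference to a first and second primary aim with the aims as now named. If the power claim is meant to cover Secondary Aim 1, restate it at 0.025, since its two measures are also tested at that level.

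The cost is wording only, with no added participants. The stated per-measure power becomes less favourable, and fixing the rule in advance gives up later freedom to interpret a split result.

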[figure not shown]
[figure not shown]
(<8mg) vs high dose (HD) (>16 mg) of buprenorphine. There was a higher dropout rate in the LD group (3/5, 60%) vs the HD group (1/4, 25%) (one participant was never randomized). Three of the drop-outs (2 in the LD group and 1 in the HD group) were lost to follow up, and one dropped out because the low dose was not effective. It is important to note that 4 out of 10 participants (40%) also had a diagnosis of PTSD in this sample. Results suggest patients prefer higher doses of buprenorphine.

Investigators in this study have had extensive clinical experience with buprenorphine ([name], [name], [name]) and [name] have had research experience in conducting clinical trials in individuals maintained on buprenorphine.

(4) Use of CPT for Veterans with PTSD and comorbid Opioid Use Disorder (OUD):

This retrospective chart review evaluated the feasibility and outcome of Veterans admitted to the examined all Buprenorphine Clinic at VA CT in West Haven to evaluate feasibility and outcomes for those with comorbid PTSD. In this study, all new buprenorphine clinic admissions between January 2016-December 2016 were identified via the electronic consult (n=103) Of those, 4 were not examined (n= 2 had a restricted record, n=2 were deceased). The remaining 99 records were evaluated for rates of comorbid PTSD, rates of referral to trauma focused treatment and retention in buprenorphine clinic after 3 months. PTSD diagnosis was evaluated using the problem list in the electronic medical record or service connection status.

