Results: Of the 99 records examined, 46 (46.5%) had the diagnosis of PTSD. Most of the Veterans were male (94.9%), with an average age of 45.3 years and majority were Caucasian (78.8%); approximately half (52.5% were single/never married. Of those with PTSD, 10 (21.5%) were referred to trauma focused treatment: of those 4 were referred to CPT, 1 was referred to Prolonged Exposure (PE), and the rest received unspecified trauma-focused therapy. Of those who received trauma-focused treatment, 4/5 (80%) completed 12 sessions. Retention at 3 months was **significantly different between groups**: of those referred to trauma focused therapy 10/10 (100%) were retained in treatment compared to 11/36 (30.5%) (p<.05) of those without referral to trauma focused therapy (See Fig 1). As a comparator, among those without PTSD (n=53) 28 were retained in treatment (52.8%). While PCL scores are not available in all cases, the n=5 who participated in the EBP had PCL scores documented in the record. *The average PCL score= 61.4 (range 53-68) at the beginning of therapy was significantly reduced to PCL= 29.2 (range 10-48) (p<.05) at the end of the 12-session intervention.* (See Fig 2)]

These studies demonstrate our group's extensive experience in the methodology proposed and our ability to recruit and safely and effectively conduct pharmacologic studies in Veterans with PTSD and comorbid substance use disorders. Further, it demonstrates our experience in conducting studies using standardized psychotherapy, notably CPT in individuals with comorbid disorders and in conjunction with pharmacotherapy.

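### The 25% dropout behind N=160 has no source, conflicts with the 30% given elsewhere in the protocol, and looks optimistic against its own retention data, so the stated 80% power is not supported

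*Combined protocol and SAP*

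**What the plan says.** The Power analysis in section 6 states that "with 60 subjects randomized to each group we have 80% power" for a medium effect (f = 0.25) "at two-sided alpha level of 0.05", and then, "assuming 25% dropout we will recruit a total of N=160". The section uses the word randomised for the 60 per group. Since 160 × 0.75 = 120, the 60 can only be the number left after dropout.

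The overview that opens Research design and methods also gives 160, but pairs it with 30% dropout and 120 participants.

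Under Data Analysis, for PTSD symptoms measured by both PCL-5 and CAPS-5, "the level of significance will be adjusted to 0.025".

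Retention data appear in D. Preliminary studies. Item (4), a chart review of new admissions to the West Haven buprenorphine clinic in 2016, assessed "retention in buprenorphine clinic after 3 months". Among patients with PTSD, 10/10 of those referred to trauma-focused therapy were retained, "compared to 11/36 (30.5%) (p<.05) of those without referral to trauma focused therapy". Among patients without PTSD, 28/53 were retained. Item (3)(b), a small open-label randomised comparison of buprenorphine doses, reports dropout of 3/5 and 1/4.

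The Exploratory Hypothesis reads: "We hypothesize that CPT will significantly improve retention (days in treatment) compared to IDC".

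**The concern.** N = 160 depends directly on the dropout rate. That rate appears with two values in the same document, and neither is tied to any evidence. The protocol holds evidence from one of its own recruiting clinics, over a window close to the 12-week treatment phase, and uses it to argue feasibility but not to set dropout. All of that evidence except very small or selected subsets points to loss above 25%.

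The calculation also applies one loss rate to both arms, while the protocol hypothesises that retention will be better with CPT. Unequal loss costs more power than the same total loss split evenly. It also puts more weight on the assumption that missing data are random, on which the mixed model relies.

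What is at stake is whether the stated power, and the number of patients expected to contribute a week-12 result, can be relied on.

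**Working it through.** **Inputs.** From the Power analysis: f = 0.25, 60 per group, two-sided alpha 0.05, 25% dropout, N = 160. From the overview: 30% dropout. From Data Analysis: alpha 0.025 for each PTSD measure. From Preliminary studies: 10/10, 11/36, 28/53, 3/5 and 1/4. Assumptions: equal allocation (80 per arm) and a completers' two-sample t-test without baseline adjustment.

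**1. The plan's own figures.** For two groups d = 2f = 0.5. With n per arm, the noncentrality is d × √(n/2) = 0.5 × √30 = 2.74 on 118 degrees of freedom. Power is 77.5% (78.2% by the normal approximation). Reaching 80% takes 64 per arm by the t-test. The stated 80% is therefore about 2 points high, which modest baseline adjustment would cover (an assumed correlation of 0.3 gives 82%). The inflation 120 / 0.75 = 160 is exact.

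**2. The two dropout figures.** 160 × 0.70 = 112, not 120. Keeping 120 after 30% loss needs 120 / 0.70 = 171.4, that is 172. The overview and the Power analysis cannot both be right.

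**3. The protocol's retention data.**

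| Group | Retained | 95% interval (Wilson) |
|---|---|---|
| PTSD, all: (10 + 11)/(10 + 36) | 21/46 = 45.7% | 32% to 60% |
| PTSD, not referred | 11/36 = 30.6% | 18% to 47% |
| No PTSD | 28/53 = 52.8% | 40% to 66% |

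These intervals all lie below 75%. They cover sampling error in clinic retention only. The dose pilot lost (3 + 1)/(5 + 4) = 4/9 = 44%. Its exact interval, 14% to 79%, is too wide to exclude 25%.

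**4. Power by loss** (d = 0.5, two-sample t, 80 randomised per arm):

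| Loss | Remaining per arm | Alpha 0.05 | Alpha 0.025 |
|---|---|---|---|
| None | 80 / 80 | 88% | 81% |
| 25%, Power analysis | 60 / 60 | 78% | 68% |
| 30%, overview | 56 / 56 | 75% | 65% |
| 54%, pooled chart review | about 36 / 36 | 56% | 44% |

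The last row uses 80 × 21/46 = 36.5 per arm.

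**5. Effect of unequal loss (illustration).** Applying the two referral subgroups to the arms leaves 80 for CPT and 80 × 11/36 = 24.4 for IDC. That is 104.4 of 160, a 35% overall loss. Power is 57% at 0.05 and 46% at 0.025. The same 104.4 split evenly (52.2 per arm) gives 72% and 61%, so the imbalance alone costs about 15 points.

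**The case against.** The strongest reply is that the chart review measured something else. It counted all new clinic admissions, took PTSD from the problem list or service connection, and recorded whether patients stayed in the clinic, not whether PTSD outcomes were missing. The Methods overview places induction before randomisation, so some early losses would fall before the trial's denominator starts. Patients already on buprenorphine skip induction. The trial adds paid visits, reminder calls, telehealth and weekly one-to-one sessions in both arms. All of this stands. A reader might infer from 21/46 that the 25% is contradicted, or that 54% is the loss to plan for. The documents support neither.

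The subgroup rates do not transfer cleanly either. Patients must stay long enough to be referred, which raises 10/10. The same mechanism puts early leavers among the unreferred and lowers 11/36. The pooled 54% also reflects a 10:36 referral mix, not two randomised arms. The 4/5 figure in the same review is completion of 12 therapy sessions, a different quantity again, and should not serve as a CPT retention rate.

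The planned analysis is an intent-to-treat mixed model on all available data, so completer power is a lower-end figure. This helps PCL-5, which is collected repeatedly during treatment. It should help less for CAPS-5, described as collected before and after treatment and at follow-up, but the documents give no correlations with which to size the gain.

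Finally, the protocol calls its effect conservative against cited effects of 1.14 and 1.69. At an assumed d of 0.7, 36.5 per arm would give 84% at 0.05 and 76% at 0.025. That is a fair point about margin, although those effects may not hold against active counselling. It does not support the 80% stated for a medium effect.

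None of these arguments appears in the protocol as the reason for 25%, and none explains the 30%.

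**Conclusion.** The concern holds in a limited form. The 25% is unsourced, conflicts with the overview's 30%, and looks optimistic against the protocol's own retention data. The stated 80% power is therefore not supported. For d = 0.5 it is 78% with 60 per arm at alpha 0.05, and 68% at the 0.025 the analysis plan applies to each PTSD measure. At the overview's 30% it is 75% and 65%. The 56% and 44% at 54% loss are a pessimistic bound, not a forecast.

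The drop from 78% to 68% comes from the alpha mismatch alone and is separate from dropout. These figures assume equal allocation, a completers' t-test and no baseline adjustment; partial PCL-5 data would raise them by an amount the documents do not allow one to calculate. The inference that the trial will keep only about 36 patients per arm goes beyond the evidence.

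**What to change.** - Reconcile the overview and the Power analysis to one dropout figure. If 30% is kept with N = 160, state 112 remaining.
- Give the source for that figure, or replace it with a sensitivity range that includes unequal loss by arm, since better retention with CPT is hypothesised. Do not use 54% as the base case.
- Restate the remaining numbers and power across the range at alpha 0.025.
- State the assumed loss from treatment separately from the assumed loss of the week-12 outcome, and note that the mixed model recovers some power from partial PCL-5 data.

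This changes protocol wording only and adds no patients. The cost is a less favourable stated power.
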